8.1.2 Pancreatitis

In the event of abdominal pain or suspected pancreatitis, amylase and lipase laboratory samples should be collected for confirmation of the diagnosis. Subjects should be closely monitored when re-starting study treatment after an episode of pancreatitis.

8.1.3 Hepatobiliary Events

8.1.3.1 Liver Chemistry Stopping Criteria

Liver chemistry stopping and increased monitoring criteria have been designed to assure subject safety and evaluate liver event etiology in alignment with the FDA premarketing clinical liver safety guidance

fda.gov/downloads/Drugs/GuidanceComplianceRegulatoryInformation/Guidances/UCM174090.pdf

8.1.3.1.1 Liver Chemistry Stopping and Increased Monitoring Algorithm for Subjects WITH entry criteria ALT ≤2.5xULN

[figure not shown]

Table 15 Liver Chemistry Stopping Criteria – Liver Stopping Event for Subjects WITH Entry Criteria ALT≤2.5xULN

ALT-absolute	ALT ≥5xULN
ALT Increase	ALT ≥3xULN persists for ≥4 weeks
Bilirubin^{1,2}	ALT ≥3xULN and bilirubin ≥2xULN (>35% direct bilirubin)
INR²	ALT ≥3xULN and INR>1.5, if INR measured
Cannot Monitor	ALT ≥3xULN and cannot be monitored weekly for 4 weeks
Symptomatic³	ALT ≥3xULN associated with symptoms (new or worsening) believed to be related to liver injury or hypersensitivity

Abbreviations: ALT, alanine aminotransferase; INR, international normalization ratio; ULN, upper limit of normal

1. Serum bilirubin fractionation should be performed if testing is available. If serum bilirubin fractionation is not immediately available, discontinue study treatment for that subject if ALT ≥3xULN **and** bilirubin ≥2xULN. Additionally, if serum bilirubin fractionation testing is unavailable, **record presence of detectable urinary bilirubin on dipstick**, indicating direct bilirubin elevations and suggesting liver injury.
2. All events of ALT ≥3xULN **and** bilirubin ≥2xULN (>35% direct bilirubin) or ALT ≥3xULN **and** INR>1.5, if INR measured which may indicate severe liver injury (possible ‘Hy’s Law’), **must be reported as an SAE (excluding studies of hepatic impairment or cirrhosis)**; INR measurement is not required and the threshold value stated will not apply to subjects receiving anticoagulants
3. New or worsening symptoms believed to be related to liver injury (such as fatigue, nausea, vomiting, right upper quadrant pain or tenderness, or jaundice) or believed to be related to hypersensitivity (such as fever, rash or eosinophilia)

8.1.3.1.2 Liver Chemistry Stopping and Increased Monitoring Algorithm including Subjects WITH Documented Liver Metastases/Tumor Infiltration at Baseline AND entry criteria ALT>2.5xULN but ≤5xULN

[figure not shown]

Table 16 Liver Chemistry Stopping Criteria – Liver Stopping Event: Subjects with Documented Liver Metastases/Tumor Infiltration at Baseline AND Entry Criteria ALT >2.5xULN but ≤5xULN

ALT-absolute	Both ALT ≥5xULN and ≥2x baseline value
ALT Increase	Both ALT ≥3xULN and ≥1.5x baseline value that persists for 4 weeks
Bilirubin^{1, 2}	ALT ≥3xULN and bilirubin ≥2xULN (>35% direct bilirubin)
INR²	ALT ≥3xULN and INR>1.5, if INR measured
Cannot Monitor	Both ALT ≥3xULN and ≥1.5x baseline value that cannot be monitored for 4 weeks
Symptomatic³	Both ALT ≥3xULN and ≥1.5x baseline value associated with symptoms (new or worsening) believed to be related to liver injury or hypersensitivity

Abbreviations: ALT, alanine aminotransferase; INR, international normalization ratio; ULN, upper limit of normal

1. Serum bilirubin fractionation should be performed if testing is available. If serum bilirubin fractionation is not immediately available, discontinue study treatment for that subject if ALT ≥3xULN and bilirubin ≥2xULN. Additionally, if serum bilirubin fractionation testing is unavailable, **record presence of detectable urinary bilirubin on dipstick**, indicating direct bilirubin elevations and suggesting liver injury.
2. All events of ALT ≥3xULN and bilirubin ≥2xULN (>35% direct bilirubin) or ALT ≥3xULN and INR>1.5, if INR measured which may indicate severe liver injury (possible 'Hy's Law'), **must be reported as an SAE (excluding studies of hepatic impairment or cirrhosis)**; INR measurement is not required and the threshold value stated will not apply to subjects receiving anticoagulants
3. New or worsening symptoms believed to be related to liver injury (such as fatigue, nausea, vomiting, right upper quadrant pain or tenderness, or jaundice) or believed to be related to hypersensitivity (such as fever, rash or eosinophilia)

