SYSTEM Adequate Baseline Organ Function	TEST	Histology	LABORATORY VALUES¹
	Total Bilirubin ⁴	BTC	≤3 times ULN if stable for 14 days prior to enrollment
		GIST, WHO Grade 1-4 Glioma, NSGCT/NGGCT, MM	≤2 times ULN
		HCL	<3 times ULN
		ASI	≤2 times ULN OR ≤3 times ULN if stable for 14 days prior to enrollment for ampullary and periampullary carcinoma
	ALT and AST ⁵	ATC, GIST, NSGCT/NGGCT	≤2 times ULN without liver metastases ≤2.5 times ULN if documented liver metastases
		BTC, ASI, MM	≤3 times ULN without liver metastases ≤5 times ULN if documented liver metastases
		HCL	<5 times ULN
		WHO Grade 1, 2, 3 or 4 Glioma	≤3 times ULN
Renal	Creatinine	ATC, BTC, GIST, WHO Grade 1-4 Glioma, NSGCT/NGGCT, ASI, HCL, MM	≤1.5 mg/dL
	OR Calculated Creatinine Clearance ⁶ or 24-hr Urine Creatinine Clearance	ATC, BTC, GIST, WHO Grade 1-4 Glioma, NSGCT/NGGCT, ASI, HCL, MM	≥50 mL/min
Cardiac	LVEF	ATC, BTC, GIST, WHO Grade 1-4 Glioma, NSGCT/NGGCT, ASI, HCL, MM	≥LLN ⁷ by ECHO

Abbreviations: ALT, alanine aminotransferase; ANC, absolute neutrophil count; ASI, adenocarcinoma of small intestine AST, aspartate aminotransferase; CBC, complete blood count; ECHO, echocardiogram; HCL, hairy cell leukemia; hr, hour; INR, international normalization n ratio; LLN, lower limit of normal; LVEF, left ventricular ejection fraction; PT, prothrombin time; PTT, partial thromboplastin time; ULN, upper limit of normal

- Laboratory values are obtained within 14 days prior to first dose of study treatment.
- PTT and PT/INR >1.5 times ULN will be acceptable in case of subjects receiving therapeutic anticoagulants such as warfarin as long as INR is monitored during the study according to clinical practice.
- HCL: No minimum CBC criteria if the cytopenias are due to disease under study.
- HCL: Subjects will be allowed to enroll with indirect hyperbilirubinemia; however, this condition must be confirmed due to hemolysis, hypersplenism or direct bilirubin ratio <35%, and requires approval from the Medical Lead.
- HCL: Subjects will be allowed to enroll with elevated ALT/AST values up to 5 times ULN; however this condition must be confirmed due to hemolysis and/or hypersplenism and not associated with hepatic dysfunction and required approval from the Medical Lead.
- Calculated by the Cockcroft-Gault formula (see [Appendix 3](#)).
- If LLN is not defined for a given institution, then ejection fraction must be ≥ 50%.

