
Subject with entry criteria ALT≤2.5xULN ALT ≥3xULN but <5xULN and bilirubin <2xULN, without symptoms believed to be related to liver injury or hypersensitivity and who can be monitored weekly for 4 weeks
 
Subject with documented liver metastases/tumor infiltration at baseline AND entry criteria ALT>2.5xULN but ≤5xULN ALT ≥3xULN and 1.5x baseline value but ALT <5xULN and 2x baseline value and bilirubin <2xULN, without symptoms believed to be related to liver injury, or hypersensitivity and who can be monitored weekly for 4 weeks
	
 • Notify the Medical Lead within 24 hrs of learning of the abnormality to discuss subject safety. • Subject can continue study treatments • Subject must return weekly for repeat liver chemistries (ALT, AST, alkaline phosphatase, bilirubin) until they resolve, stabilise or return to within baseline • If at any time subject meets the liver chemistry stopping criteria, proceed as described above 
For subjects with entry criteria ALT≤2.5xULN
 
 • If, after 4 weeks of monitoring, ALT <3xULN and bilirubin <2xULN, monitor subjects twice monthly until liver chemistries normalize or return to within baseline. 
For subjects with documented liver metastases/tumor infiltration at baseline AND entry criteria ALT>2.5xULN but ≤5xULN
 
If, after 4 weeks of monitoring, ALT <3xULN and <1.5x baseline value, and bilirubin <2xULN, monitor subjects twice monthly until liver chemistries normalize or return to within baseline

Refer to [Appendix 18](#) for liver safety drug restart or rechallenge guidelines.

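### Tables 15, 16 and 18 place subjects admitted with ALT above 2.5xULN and no documented liver metastases or infiltration in no liver stopping or monitoring group

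*Protocol*

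**What the plan says.** Protocol 8.1.3.1 divides subjects by ALT at entry.

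- Section 8.1.3.1.1 and Table 15 are for one group: "Liver Chemistry Stopping and Increased Monitoring Algorithm for Subjects WITH entry criteria ALT ≤2.5xULN".
- Section 8.1.3.1.2 is headed "Algorithm including Subjects WITH Documented Liver Metastases/Tumor Infiltration at Baseline AND entry criteria" above 2.5 and up to 5xULN. Table 16 beneath it is titled for "Subjects with Documented Liver Metastases/Tumor Infiltration at Baseline AND Entry Criteria ALT" in that range, so both conditions must be met.
- Table 18 (8.1.3.1.3) repeats the split. Its second group reads "For subjects with documented liver metastases/tumor infiltration at baseline AND entry criteria ALT>2.5xULN but ≤5xULN".
- Table 17 lists what follows a liver stopping event: immediate discontinuation, a defined work-up, weekly or twice-weekly chemistry, and no rechallenge without Medical Governance approval. Such events are defined in Tables 15 and 16. The liver criterion in 16.2 points back to 8.1.3.1 and adds no group.

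Table 3 (5.4.1) sets the entry limits by cohort. HCL may enter with ALT/AST up to 5xULN where "this condition must be confirmed due to hemolysis and/or hypersplenism and not associated with hepatic dysfunction", with Medical Lead approval. The note after Table 3 also lets in subjects whose AST, ALT or bilirubin is out of range because of Gilbert's syndrome or asymptomatic gallstones.

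**The concern.** The entry criteria and the liver rules do not partition the same population. A subject can be eligible with ALT above 2.5xULN and no documented liver metastases or infiltration, and then belong to neither stopping group and neither monitoring group.

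The case that matters most is a possible Hy's Law event. ALT ≥3xULN with bilirubin ≥2xULN (>35% direct), or with INR >1.5, is a stop under both Table 15 and Table 16. For the unassigned subjects it is not a stop by the stated scope, and the Table 17 work-up, monitoring frequency and rechallenge barrier are not set in motion. Action then depends on investigator attribution and judgment, against a routine chemistry schedule of every 4 weeks (Table 4).

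**Working it through.** The plan gives no figure on this point, so the check compares the scopes.

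**1. Entry limits against table scope.** Limits are ALT in xULN from Table 3. Table 15 covers ≤2.5. Table 16 covers >2.5 to ≤5 with documented liver metastases or infiltration.

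| Cohort | Limit without liver metastases | Limit with | Admitted but unassigned |
|---|---|---|---|
| ATC, GIST, NSGCT/NGGCT | 2 | 2.5 | none |
| BTC, ASI, MM | 3 | 5 | >2.5 to 3, no metastases |
| Glioma grade 1-2, grade 3-4 | 3 (no metastasis condition) | same | >2.5 to 3, no metastases |
| HCL | <5 (no metastasis condition) | same | >2.5 to <5, no documented infiltration |

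Cohorts with a gap: 3 + 2 + 1 = 6 of 9. The Gilbert's/gallstones note can add subjects from any cohort. With documented metastases or infiltration, every cohort is covered by its Table 3 limit. If entry criteria is taken to mean the cohort's limit rather than the subject's own value, the gap widens: all metastasis-free BTC, ASI and MM subjects, and all glioma and HCL subjects without documented infiltration, fall outside Table 15.

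**2. The same event in each group.** Take ALT ≥3xULN with bilirubin ≥2xULN (>35% direct).

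- Table 15 or 16 subject: liver stop, so Table 17 applies.
- Unassigned subject: protocol-specific SAE under 11.2, reported within 24 hours under 11.12. No liver stop is assigned, so Table 17 is not triggered.

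**3. Reach.** The Amendment 11 rationale gives 55 subjects on treatment on 06-Apr-2020. In the six cohorts: 36 HCL + 10 glioma grade 3-4 + 6 glioma grade 1-2 + 1 BTC = 53. The other 55 − 53 = 2 (ATC) could be affected only through the Gilbert's/gallstones note. These are cohort counts; entry ALT is not reported.

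**4. Which criteria carry over.** The bilirubin and INR rows are identical in Tables 15 and 16 and contain no baseline term, so they extend without a new threshold. The ALT-only rows do not. With entry ALT b:

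- Table 15, any b: 3xULN persisting ≥4 weeks, and 5xULN absolute. An HCL subject entering at 3 to <5xULN already meets the 3xULN level.
- Table 16: persistent stop max(3, 1.5b), absolute stop max(5, 2b). At b = 3 these are 4.5 and 6; at b = 4.9 they are 7.35 and 9.8.

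One is too tight for HCL at baseline and the other lets ALT rise far. The choice is a safety judgment.

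**5. A side effect of extending the bilirubin stop.** HCL may enter with ALT <5xULN and bilirubin <3xULN when the hyperbilirubinemia is indirect. An entry ALT ≥3xULN with total bilirubin ≥2xULN meets both limits on day 1, and only the >35% direct condition prevents a stop. Footnote 1 to both tables removes that condition: "If serum bilirubin fractionation is not immediately available, discontinue study treatment for that subject if ALT" is ≥3xULN and bilirubin ≥2xULN. Table 6 already requires direct bilirubin when total is ≥2xULN, so requiring fractionation adds little.

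**The case against.** Three arguments have weight.

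**Scope.** Both algorithm figures are missing from the available text, and the 8.1.3.1.2 heading uses the word *including*, which may point to a wider group. That stands as a limit. However, Tables 16 and 18, which carry the thresholds, state the restriction without that word.

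**Other controls.** A reader might infer that these subjects have no liver protection, or would stay on treatment through a Hy's Law event. The documents do not support that. Section 1.4 calls for withdrawal on clinically significant toxicity. Section 16.2 stops treatment for unacceptable toxicity, with the liver criteria as one instance. Section 7.4.8 requires abnormal values to be repeated and, if they do not normalize, the etiology sought and the Medical Lead told. Section 11.11 obliges supplemental investigation of SAEs. Nor does Table 11 simply return a subject to treatment at a lower dose: after Grade 3 it allows restart only once the event has resolved to ≤Grade 1, and Medical Lead approval is needed after ≥21 days. What these provisions lack is an automatic stop and a prescribed work-up. Table 11 also applies only to events the investigator considers treatment-related.

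**Reach.** HCL subjects with raised ALT were individually vetted by the Medical Lead, and enrollment closed on 29-Jun-2018. It would be wrong to read 53 of 55 as the number left uncovered.

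**Conclusion.** The gap is real on the stated scope of Tables 15, 16 and 18. It covers entry ALT >2.5 to 3xULN in five cohorts and >2.5 to <5xULN in HCL, all without documented metastases or infiltration, plus subjects admitted through the Gilbert's/gallstones note. Its consequence is limited but specific: a possible Hy's Law event must be reported but does not automatically stop treatment or start the Table 17 actions, so these subjects have weaker liver rules than others in the same trial. The conclusion assumes that the unseen figures do not widen the groups. The number of subjects affected is unknown and may be zero. Priority is low to moderate.

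**What to change.** 1. State in 8.1.3.1 that the bilirubin and INR stopping criteria and the Table 17 actions apply to all subjects, whatever their entry ALT or metastasis status.
2. For HCL subjects admitted with indirect hyperbilirubinemia, require fractionation before the bilirubin stop is applied, so that footnote 1 cannot stop a subject at an admitted baseline.
3. Have the sponsor's safety physicians assign ALT-only stopping and monitoring thresholds for this group. Keep Table 11 in force until they do.

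The cost is a short protocol amendment and extra liver work-up in the few subjects who meet the criteria.

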8.1.3.1.3 Liver Safety Required Actions and Follow-Up

Table 17 Required Actions and Follow-Up Assessments Following ANY Liver Stopping Event

Actions	Follow-Up Assessments

 • Immediately discontinue study treatments • Report the event to the sponsor within 24 hrs • Complete the liver event eCRF and complete an SAE data collection tool if the event also meets the criteria for an SAE² • Perform liver event follow-up assessments • Monitor the subject until liver chemistries resolve, stabilize, or return to within baseline (see MONITORING below) • Do not restart/rechallenge subject with study treatment unless allowed per protocol and the sponsor Medical Governance approval is granted (refer to Appendix 18) 	
 • Viral hepatitis serology¹ • Only in those with underlying chronic hepatitis B at study entry (identified by positive hepatitis B surface antigen) quantitative hepatitis B DNA and hepatitis delta antibody³. • Blood sample for PK analysis, obtained 24-72 hrs after last dose⁴ • Serum creatine phosphokinase and lactate dehydrogenase. • Fractionate bilirubin, if total bilirubin ≥2xULN • Obtain complete blood count with differential to assess eosinophilia • Record the appearance or worsening of clinical symptoms of liver injury, or hypersensitivity, on the AE eCRF • Record use of concomitant medications on the concomitant medications report

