- EC or IRB approval for rechallenge with study treatment must be obtained, as required.
- If the rechallenge is approved by Novartis Medical Governance in writing, the subject must be provided with a clear description of the possible benefits and risks of study treatment administration, including the possibility of recurrent, more severe liver injury or death.
- The subject must also provide signed informed consent specifically for the rechallenge with study treatment. Documentation of informed consent must be recorded in the study chart.
- Study treatment must be administered at the dose specified by the sponsor.
- Subjects approved by Novartis Medical Governance for rechallenge with study treatment must return to the clinic twice a week for liver chemistry tests until stable liver chemistries have been demonstrated and then standard laboratory monitoring may resume as per protocol.
- If after study treatment rechallenge, subject meets protocol-defined liver chemistry stopping criteria, study treatment should be permanently discontinued.
- Medical Lead, and the IEC or IRB as required, must be informed of the subject's outcome following study treatment rechallenge.
- The sponsor to be notified of any AEs, as per Section 11.

2. Restart Following Transient Resolving Liver Stopping Events NOT Related to Study Treatment

Restart refers to resuming study treatment following liver stopping events in which there is a clear underlying cause (other than DILI) of the liver event (e.g. biliary obstruction, pancreatic events, hypotension, acute viral hepatitis). Furthermore, there should be no evidence of alcoholic hepatitis or hypersensitivity, and the study treatment should not be associated with HLA markers of liver injury.

Approval by the sponsor for study treatment restart can be considered where:

- Investigator requests consideration for study treatment restart if liver chemistries have a clear underlying cause (e.g., biliary obstruction, hypotension and liver chemistries have improved to normal or are within 1.5x baseline and ALT <3xULN).
- Restart risk factors (e.g. fever, rash, eosinophilia, or hypersensitivity, alcoholic hepatitis, possible study treatment-induced liver injury or study treatment has an HLA genetic marker associated with liver injury (e.g. lapatinib, abacavir, amoxicillin/clavulanate) are reviewed and excluded.
- IEC or IRB approval of study treatment restart must be obtained, as required.

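### For some BTC and ampullary or periampullary ASI subjects with liver metastases, the Table 16 bilirubin row is already met by eligible entry values, and SAP 2.7.3 does not separate these from on-treatment rises (minor)

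*Protocol*

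**What the plan says.** Entry limits (Protocol Section 5.4.1, Table 3):

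- BTC subjects may enter with total bilirubin up to 3×ULN if it has been stable for 14 days. ASI subjects have the same allowance only for some primaries: "≤3 times ULN if stable for 14 days prior to enrollment for ampullary and periampullary carcinoma".
- ALT and AST for BTC, ASI and MM may be "≤5 times ULN if documented liver metastases".
- No limit on the direct fraction applies to BTC or ASI. For HCL, a footnote ties high entry bilirubin to hemolysis, hypersplenism or a direct ratio below 35%.

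Stopping rules (Section 8.1.3.1.2, Table 16):

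- The bilirubin row is "ALT ≥3xULN and bilirubin ≥2xULN (>35% direct bilirubin", with no baseline term. The INR row is also absolute.
- The other four rows add a baseline multiple of 1.5 or 2. The ALT-increase row, for example, reads "Both ALT ≥3xULN and ≥1.5x baseline value that persists for 4 weeks".
- Footnote 1 widens the bilirubin row: "If serum bilirubin fractionation is not immediately available, discontinue study treatment for that subject" at the same ALT and total bilirubin values.
- Footnote 2 and Section 11.2 item h make the combination an SAE, but keep the 35% direct condition.

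Consequences:

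- After any liver stopping event Table 17 says "Immediately discontinue study treatments".
- Table 18 lets subjects with liver metastases continue under monitoring only at "ALT ≥3xULN and 1.5x baseline value but ALT <5xULN and 2x baseline value and bilirubin <2xULN".
- Appendix 18 offers restart or rechallenge with sponsor approval.

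Reporting: SAP 2.7.3 counts combined ALT or AST and bilirubin elevations on peak on-therapy values that need not be concurrent. It gives 3×ULN as an example threshold, but no bilirubin cut-off for the combined criteria and no baseline condition.

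**The concern.** A stopping rule should respond to a change on treatment. Here a subject can qualify for the study and meet a mandatory stopping rule with the same pair of values. The protocol recognises the problem for ALT, since it baseline-adjusts the rows that use ALT without bilirubin or INR. The bilirubin row, however, is the same as in Table 15, which is written for subjects entering at ALT up to 2.5×ULN.

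Two things are at stake. An eligible subject could lose study treatment, and above 35% direct be reported as a possible Hy's Law case, because of disease present at entry. In the final report, the combined ALT and bilirubin count could then mix baseline liver disease with possible drug injury. The study is single-arm, so no control group would reveal this.

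**Working it through.** The plan gives no figure to reproduce, so the check sets the entry limits against the stopping rows.

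**1. Overlap.** Table 16 applies at entry ALT >2.5 to 5×ULN. Its bilirubin row needs ALT ≥3 and bilirubin ≥2. Table 3 caps entry at ALT 5 and bilirubin 3. The overlap is ALT 3.0–5.0×ULN with bilirubin 2.0–3.0×ULN, for BTC and for ampullary or periampullary ASI. Other ASI and MM (bilirubin cap 2×ULN) touch the trigger only at exactly 2.0. ATC, GIST and NSGCT/NGGCT cannot enter Table 16, because their ALT cap is 2.5×ULN.

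**2. One subject, values unchanged (ALT 4, bilirubin 2.5×ULN).**

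| Direct fraction | Bilirubin row | Item h SAE |
|---|---|---|
| 50% | met: discontinue | met |
| not immediately available | met through footnote 1: discontinue | not met |
| 30% | not met | not met |

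The ALT-absolute row would need ALT ≥2 × 4 = 8. The ALT-increase row would need ≥1.5 × 4 = 6. Neither is met. Item g for pre-existing liver disease (ALT ≥8 and bilirubin ≥5) is not met either.

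**3. Ways back.** Table 18 needs bilirubin below 2×ULN, so it is closed. Restart after an unrelated event (Appendix 18, part 2) gives ALT below 3×ULN as its example condition, which this subject did not meet at entry. Rechallenge after a possibly related event (part 1) has no such limit, but "If after study treatment rechallenge, subject meets protocol-defined liver chemistry stopping criteria, study treatment should be permanently discontinued", and unchanged values meet the criteria again.

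**4. Grid.** Take entry ALT 2.6–5.0 (25 values) and bilirubin 0.5–3.0 (26 values) in steps of 0.1: 25 × 26 = 650 points, all assumed above 35% direct or unfractionated. The rule tested is the secondary fix below: where baseline bilirubin is ≥2×ULN, the row also requires ALT or bilirubin ≥1.5× baseline.

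| ALT change | Bilirubin change | Stops as written | Stops with the fix |
|---|---|---|---|
| ×1.0 | ×1.0 | 21 × 11 = 231 | 0 |
| ×1.0 | ×1.4 | 21 × 16 = 336 | 21 × 5 = 105 |
| ×1.0 | ×1.5 | 21 × 17 = 357 | 357 |
| ×1.5 | ×1.0 | 25 × 11 = 275 | 275 |
| ×1.4 | ×1.4 | 25 × 16 = 400 | 25 × 5 = 125 |
| ×1.5 | ×1.5 | 25 × 17 = 425 | 425 |

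Stops at unchanged values disappear, and every stop at a 1.5-fold rise in either test is kept. The cost shows between the two. With both tests at ×1.4, 400 − 125 = 275 stops are deferred: 231 points that began at or above 3×/2×, and 4 × 11 = 44 that began at ALT 2.6–2.9 with bilirubin ≥2 and crossed ALT 3 on treatment.

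New thresholds: entry 4/2.5 stops at ALT 6.0 or bilirubin 2.5 × 1.5 = 3.75. Entry 5/3 stops at 7.5 or 4.5. Entry 2.9/2.5, which now stops at ALT 3.0 (3.0/2.9, a 3% rise), would stop at 2.9 × 1.5 = 4.35 or 3.75.

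These counts describe a region of values. They are not a probability.

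**The case against.** The strongest case is that the row is deliberate. Bilirubin and INR are the two possible Hy's Law rows, and both stay absolute while the other four are adjusted. Section 8.1.3.1 says the criteria follow FDA liver-safety guidance, and Section 1.4 reports no clinical data in moderate or severe hepatic impairment. This is a fair reason for caution and for keeping the row absolute for most subjects. It does not explain admitting subjects who already meet the rule.

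Further objections, and what stands of each:

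- *SAE reporting.* Section 11.1 excludes fluctuations of pre-existing conditions that do not worsen. Section 11.3 excludes disease-related findings unless more severe than expected. Footnote 2 nevertheless makes reporting mandatory. The result is conflicting instructions, not a clear duty to report.
- *SAP displays.* The eDISH plot is by cohort, and subject-level time courses of ALT, AST, ALP and bilirubin are planned, so a high flat baseline would be visible. This stands in part: the combined count is still not split, and the baseline-referenced grade tables take one test at a time.
- *Timing.* Enrollment ended on 29-Jun-2018. At 06-Apr-2020 one BTC subject was on treatment, five were in follow-up, and no ASI subject was listed in either group. Chemistry is checked every 4 weeks, so a subject with triggering entry values should have met the row early. This stands, and it makes the protocol change secondary.
- *Narrow group.* BTC subjects with unrelieved biliary obstruction are excluded (Section 5.4.2.1.2). This reduces the group but leaves the 3×ULN limit.

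**Conclusion.** The point holds and is minor. For BTC and ampullary or periampullary ASI subjects under Table 16, ALT 3–5×ULN with bilirubin 2–3×ULN is both eligible and a stopping event at unchanged values, given direct bilirubin above 35% or no prompt fractionation.

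A reader might infer more than the documents support:

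- *The whole bilirubin row lies within the entry limits.* It does not. The trigger has no upper bound, and only this corner overlaps.
- *Every such stop is also an SAE.* Only above 35% direct. The unfractionated branch is a discontinuation rule alone.
- *These subjects become non-responders.* Disease assessments continue after discontinuation (Section 16.3) and count until progression or new therapy (SAP 2.4.3). The ORR effect is at most a possible lost response.
- *Subjects were wrongly stopped.* The documents do not say how many, if any, entered in this region.

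The conclusion rests on the literal tables; the algorithm figure in Section 8.1.3.1.2 could not be read. The main remaining exposure is interpretation of the final hepatic tables.

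**What to change.** **Main change, SAP 2.7.3.**

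- State the combined cut-offs: ALT or AST ≥3×ULN with bilirubin ≥2×ULN.
- Split the combined counts, and mark the eDISH points, by whether the subject was already at or above both cut-offs at baseline.
- List BTC and ASI subjects discontinued for a liver event, or reported with a liver SAE, while ALT and bilirubin were both below 1.5× baseline.

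The cost is one sentence, one split and one listing. The data should already be held: Table 6 requires direct bilirubin when total bilirubin is ≥2×ULN.

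**Secondary change, protocol, for any subject still on treatment and subject to the sponsor's hepatic safety review.**

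- For Table 16 subjects with baseline bilirubin ≥2×ULN, whether baseline ALT is just below or above 3×ULN, add to the bilirubin row, its footnotes and item h: *and ALT or bilirubin ≥1.5× baseline*.
- Keep these subjects on the Table 18 schedule, weekly for 4 weeks and then twice monthly, so that they are not left unmonitored.
- Leave the row absolute for everyone else, and leave item g as it is.
- State that item h takes precedence over Section 11.3 only when this rise is present.

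The downside is a somewhat later stop for the few subjects with high baseline bilirubin: at most ALT 7.5×ULN or bilirubin 4.5×ULN on this row, for entry at the 5/3 limit.
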